9.2.2 Selection criteria

The study population will consist of all patients, newly initiated on Rivaroxaban or Phenprocoumon with an NVAF diagnosis meeting the following inclusion and exclusion criteria

Inclusion criteria:

- First dispense date of Rivaroxaban (15mg or 20mg - PZN based) or Phenprocoumon (PZN based) between January 1, 2012 and December 31, 2015
- At least two verified outpatient diagnoses or one inpatient diagnosis (main or secondary diagnosis) of NVAF (ICD-10 GM I48.0/ I48.1/I48.2/I48.9) in the individual time frame of 4 quarters before the index date (pre-index period) or within the index quarter
- Patients will be required to have 4 quarters of enrollment for the assessment of baseline characteristics and be observable and insured in the database for at least one day after their individual index date (post-index period)
- ≥ 18 years of age

Exclusion criteria:

- Patients with valvular AF [4 quarters prior to the index date] (see Table 5)
- Pregnancy [4 quarters prior to index date]

- Malignant cancers [4 quarters prior to the index date or “condition after”] (see Table 10)
- Transient cause of AF [4 quarters prior to index date] (see Table 5)
- Patients with VTE (pulmonary embolism or DVT) [60 days before index] (see Table 10)
- Patients with major surgery defined as hip or knee replacement [60 days before index] (see Table 10)
- Prescriptions of OACs (Rivaroxaban, VKA, Dabigatran, Apixaban) before index date [4 quarters prior to index date] (see Table 3, Table 4)
- Patients receiving more than one anticoagulant substance (Apixaban, Dabigatran, Rivaroxaban or Phenprocoumon) or more than one dosage of a substance on the index date (see Table 3, Table 4)
- *For sensitivity analysis* ([see data analysis section](#)) : Patient with any of the events defined in the combined endpoints [4 quarters prior to index date or “condition after”] (see Table 6)
- Patients with dialysis [4 quarters prior to index date] (see Table 10)

[figure not shown]

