Hypertension	categorical	Ambulatory verified diagnoses in the four quarters prior to the index quarter as well as primary and secondary hospital discharge diagnoses within the 365 days before or on the index date will be used assess whether patients suffered from hypertension. Hypertension will be defined using the ICD-10 GM code I10.*.
Congestive heart failure	categorical	Ambulatory verified diagnoses in the four quarters prior to the index quarter as well as primary and secondary hospital discharge diagnoses within the 365 days before or on the index date will be used assess whether patients suffered from congestive heart failure. Congestive heart failure will be defined using the ICD-10 GM code I50.*.

Atherosclerosis of arteries of extremities	categorical	Ambulatory verified diagnoses in the four quarters prior to the index quarter as well as primary and secondary hospital discharge diagnoses within the 365 days before or on the index date will be used assess whether patients suffered from peripheral vascular disease. Peripheral vascular disease will be defined using the ICD-10 GM code I70.2.
Ischemic stroke or TIA during baseline	categorical	Ambulatory verified diagnoses in the four quarters prior to the index quarter as well as primary and secondary hospital discharge diagnoses within the 365 days before or on the index date will be used assess whether patients suffered from ischemic stroke or TIA. Ischemic stroke or TIA will be defined using the ICD-10 GM code I63, I64, G45.9 and G45.8.
Coronary heart disease	categorical	Ambulatory verified diagnoses in the four quarters prior to the index quarter as well as primary and secondary hospital discharge diagnoses within the 365 days before or on the index date will be used assess whether patients suffered from coronary heart disease. Coronary heart disease will be defined using the ICD-10 GM code I20*(angina pectoris), I24.*(other acute ischemic heart diseases) and I25* (chronic ischaemic heart disease).
Liver disease		
Mild liver disease	categorical	Ambulatory verified diagnosis in the four quarters prior to the index quarter as well as primary and secondary hospital discharge diagnoses within the 365 days before or on the index date will be used assess whether patients suffered from a mild liver disease. Mild liver disease will be defined using the ICD-10 GM codes according to the Charlson Comorbidity Index (Table 8).

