We will perform 1:1 nearest-neighbor matching. After matching, we expect to see balance between the Rivaroxaban and VKA groups with respect to all measured factors. To ensure this, we will examine propensity score balance diagnostics including: (1) pre- and post-matching propensity score overlap plots; (2) pre- and post-matching c-statistics and (3) pre- and post-standardized mean differences (SMD) between the two treatment groups.

Patient time under risk and censoring

Patients will be censored in the follow-up period as follows:

Patients will be followed from index date to date of discontinuation of treatment, switch of treatment, death, end of continuous enrollment in the sick fund or end of study period without experiences any event, whichever occurs first.

Sensitivity Analyses

For this study sensitivity analyses are planned according to dosing regimen and patients with prior events of any of the events defined in the combined endpoints.

One separate analysis will be conducted for patients receiving 20mg Rivaroxaban only (standard-dose analysis). Patients will be censored once a different dose was prescribed compared to the index dose of 20mg. For patients receiving initiating 15mg Rivaroxaban baseline characteristics will be outlined descriptively.

Additionally, a separate analysis will be planned where patients with any of the events defined in the combined endpoints within the baseline period 4 quarters prior to index date or “condition after”) will be included in the analyses.

Therefore, sensitivity analyses will result in four separate cohort and patient time datasets for which a propensity score matching and a multivariate analysis will be performed.

Handling of Missing Data

Missing data will not be imputed.

Statistical Software

All analyses will be performed with SAS 9.2.

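### Sections 9.2.2 and 9.7.1.2 point in opposite directions on whether patients with prior endpoint events belong in the main cohort, and no dataset is named as primary

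*Protocol*

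**What the plan says.** **Section 9.2.2, exclusion criteria.** One bullet is labelled as being for sensitivity analysis and refers the reader to the data analysis section. It names "Patient with any of the events defined in the combined endpoints", with a look-back of four quarters before the index date or a condition-after diagnosis, and takes its codes from Table 6.

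**Section 9.7.1.2, Sensitivity Analyses.** The opening sentence says that "sensitivity analyses are planned according to dosing regimen and patients with prior events of any of the events defined in the combined endpoints". The specific sentence then says that "a separate analysis will be planned where patients with any of the events defined in the combined endpoints within the baseline period", with the same look-back, "will be included in the analyses". The paragraph closes by saying that "sensitivity analyses will result in four separate cohort and patient time datasets", each with its own propensity score matching and multivariate analysis. It does not say which of the four is the main one.

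**Section 9.7, opening.** The protocol states that analysis populations are adequately described in this section and that no separate SAP will follow.

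**Table 2.** The covariate list contains "Ischemic stroke or TIA during baseline".

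**The concern.** The two sections give opposite rules for the same patients. Section 9.2.2 ties their exclusion to the sensitivity analysis; section 9.7.1.2 ties their inclusion to it.

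The choice sets the population for both primary endpoints. One version describes eligible NVAF initiators whether or not they have a recent or recorded stroke, intracranial haemorrhage, TIA or Table 6 embolic event. The other describes only those without one. Event counts will differ and the hazard ratios may differ. Section 9.9 says that the results are valid only for the population defined by the selection criteria, and on this criterion that population is not fixed.

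Both versions will be analysed in full. With no primary dataset named, either could be reported as the main result and the other as the sensitivity analysis, and each choice could cite the protocol.

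**Working it through.** **1. The two rules side by side.**

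| | Section 9.2.2 | Section 9.7.1.2 |
|---|---|---|
| Patients | Any event of the combined endpoints | Any event of the combined endpoints |
| Look-back | 4 quarters before index, or condition-after | 4 quarters before index, or condition-after |
| Action in the sensitivity analysis | Excluded | Included |
| Implied main cohort | Keeps them | Omits them |

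Only the action differs. The implied main cohort is an inference in both columns, but it is the natural one: a sensitivity analysis defined by a change to the cohort implies that the main analysis lacks that change.

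**2. Does anything else decide it?**
- The opening sentence on sensitivity analyses names prior events as a dimension and gives no direction.
- Four datasets fit a 2 x 2 layout (dose by prior-event status) under either rule.
- Section 9.5 cuts the feasibility counts by up to 25%: 22,800 x 0.75 = 17,100 and 39,600 x 0.75 = 29,700, which reproduces the stated 17,000 and 30,000 after rounding. It does not say whether this criterion is part of the cut.
- Section 9.7 rules out a separate SAP, so the question cannot be left to one.

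**3. Which way does the rest of the protocol lean?** Table 6 defines the events by I63 (ischaemic stroke), I60-I62 (ICH), I26 and I80.1/.2/.3/.9 (labelled SE), and G45.8/G45.9 (TIA).
- Baseline stroke/TIA covariate (Table 2): I63, I64, G45.8, G45.9. Excluding Table 6 events would leave only I64.
- HAS-BLED stroke item (Table 9): I63 only. It would be zero for essentially everyone.
- VTE exclusion (section 9.2.2): 60 days, with Table 10 codes I26 and I80-I82 without I80.0. If I26 and the main I80 codes were already excluded over four quarters, this shorter rule would be largely redundant. It would add only the I80-I82 codes outside Table 6.

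Each item fits a main cohort that keeps these patients.

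**4. Size.** The protocol gives no prevalence of prior events and no event rate by history, so both inputs here are assumptions. Let x be the share of initiators with a qualifying prior event and r their event rate relative to the others. Their share of all outcome events is x·r / (x·r + 1 − x).
- x = 0.05, r = 2: 0.10 / 1.05 = 9.5%
- x = 0.10, r = 2: 0.20 / 1.10 = 18%
- x = 0.10, r = 3: 0.30 / 1.20 = 25%
- x = 0.20, r = 3: 0.60 / 1.40 = 43%

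The top figure pairs both upper extremes. The qualifying group also includes patients who enter through I26 or I80 codes, for whom a rate ratio of 2-3 is a further assumption.

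**The case against.** The best defence is that the two passages can be reconciled. The bullet in section 9.2.2 stands in the exclusion list and defers to the data analysis section. It could mean an exclusion that is varied in the sensitivity analysis, in which case the main cohort omits these patients and section 9.7.1.2 describes the analysis that restores them. This is coherent, but the label would have to mean that the exclusion applies in the main analysis only, which is not what it says. Another loose reading, that the separate analysis is restricted to patients with prior events, is not stated either. Figure 1, on selection of the study population, is not available here and might show the intention, but it could not make the two texts agree.

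A reader might also infer that the main cohort must include these patients because the baseline stroke variables, the risk scores and the comorbidity tables would otherwise be empty. The code lists do not support that. I64 stays in the Table 2 covariate. The stroke item of CHADS2 and CHA2DS2-VASc (Table 7) keeps I64, I69, I74 and other codes. The I64 row of Tables 21 and 28 survives, and the G45 row survives in part. What would empty is narrower: the HAS-BLED stroke item and rows such as I61, I62 and I63. Any analysis that includes these patients needs the variables anyway, so their presence does not identify the primary cohort. This part of the defence stands.

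It would likewise be too strong to call the alternative cohort a primary-prevention population. The criterion reaches back four quarters or to a condition-after diagnosis, leaves I64 and I69 histories in, and removes pulmonary embolism and deep-vein thrombosis through the Table 6 codes.

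**Conclusion.** The contradiction stands and must be resolved before data access. On the literal text, section 9.2.2 keeps patients with prior combined-endpoint events in the main cohort and section 9.7.1.2 omits them. Nothing else in the readable protocol names the primary dataset.

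The direction is supported but not settled. The wording of section 9.2.2 and the items in step 3 of the working favour keeping these patients in the main analysis. They do not exclude that the sponsor intended the opposite.

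No numerical size can be claimed. The range of about 10-43% of events rests wholly on an assumed prevalence of 5-20% and an assumed rate ratio of 2-3. A reader might go on to infer a matching loss of power, but the protocol does not support a figure, because section 9.5 does not say whether these patients were counted.

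**What to change.** Before data access, make sections 9.2.2 and 9.7.1.2 state the same rule for patients with prior combined-endpoint events, and name which of the four datasets is primary for ischaemic stroke and ICH.

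If the main analysis keeps these patients, which the rest of the protocol favours, change included to excluded in the sensitivity sentence of section 9.7.1.2. If the sponsor intended the opposite, leave section 9.7.1.2 as it is and rewrite the bullet in section 9.2.2 as an exclusion for the main analysis. In either case check that Figure 1 shows the same rule.

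The cost is a few words in one or both sections. All four datasets are already planned, so no new data or analysis is needed. Section 6 gives the same date for the final protocol and the start of analysis, so the correction belongs in the final protocol.

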9.8 Quality control

Data quality management comprises data collection, management, and verification processes, including quality control processes and documentation of the quality control steps. Data quality management is built in to the core processing systems. In addition SAS is used to process data extracted from the production process to determine quality metrics.

As part of the management strategy the HRI documents and implements:

1. Quality control processes around reference data
2. Rules for raw data checks for completeness reasonability and volume
3. Control processes for production files and outputs
4. Process flow and maintenance processes including standard operating procedures
5. Database metrics including quality and completeness
6. Procedures for handling internal inquiries.

The HRI routinely applies data quality assurance across data life-cycle stages. The following process is typical:

Data acquisition

The acquisition of the data follows a predefined statistical data-collection design/plan. The first control is the assurance that this plan is executed, i.e. all the required data items have been acquired and are in the collected-data-repository.

Data completeness checks

1. Checking the file for completeness
2. Ensuring the file format consistency with a predefined standard
3. Checking the file for data content (e.g. check for corresponding values in each field).

Data-processing checks

1. Control for correctness of the format and any input files format transformations
2. Control of correctness of the bridged data.

Processed-data checks

1. Control of individual data-suppliers - total data volume versus expected and previous periods
2. Checks for missing data estimations
3. Check for aggregated data by analysis unit, e.g. values for surgeries, hospitals, regions.

Indicator Quality Assurance

The HRI will provide a series of descriptive statistics derived from the underlying data to validate the integrity of the field content. A sample of these statistics includes but is not limited to:

1. Record counts with each data table
2. Unique counts of patients
3. Unique counts of patients continuously enrolled for specified one year increments
4. Percentage of missing values in key data fields (e.g. patient date of birth, patient gender, billing and diagnosis codes, dates of service, etc.)
5. Percentage of valid values in key data fields
6. Verify that a unique patient identifier is linked to only one individual.

9.9 Limitations of the research methods

As with any data source, the HRI research database has limitations. Some have to do with the nature of claims data and others with the nature of the German sick funds claims.

Key limitations include:

- The HRI research database is based on a large sample. Because the sample is not random, it may contain biases or fail to generalize well to other populations. However, these data can complement other datasets or be used as benchmarks against them.
- For the comorbidities of interest, the level of precision in the coding system of the database may impact the level of precision of the results and also, may limit the comparability of results across databases. The proportions of patients with a given comorbidity may differ greatly, only due to the structure of the diagnosis coding system. Also, the reason for prescribing is not captured.
- Claims data are recorded for accounting purposes and not for clinical research. As a result, it is not possible to characterize patients by clinical parameters or to see the physician's intention for each intervention.
- The HRI research databases do not provide information on lifestyle variables such as smoking, but recording of lifestyle factors should be non-differential with respect to exposure, and PS matching is expected to generate balance between cohorts on

measured confounders (some of which will strongly correlate with unmeasured factors).

- In Germany, outpatient data is only delivered on a quarterly basis. Date of diagnosis is not available, only the quarter of diagnosis.
- The results which will be derived from this study are only valid for the population described by the in- and exclusion criteria.

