Prescription medications of relevant comedications including anticoagulation therapy, antiarrhythmic drugs, and other medications (see Annex 2, Table 13) in the individual 4 quarters before the index quarter (pre-index period) will be assessed.

Table 2 – Definition of covariates

Variable	Category	Operational definition
Age	continuous	Age in the index quarter.
Gender	categorical	Sex on the index date.

Insurance status	categorical	
Insurance status on the index date:
 
 • regular insurance • retired • family insured • unknown
Number of hospitalizations	continuous	Total number of hospitalizations, independent of admission diagnosis, during the baseline period.
No of unique medications	continuous	Number of unique pharmaceutical substances (unique ATC 5 Codes) per patient received during the baseline period, based on the prescriptions documented in the database.
Interactions with co-medications	categorical	
In order to determine whether patients were concurrently treated with other medication interacting with Rivaroxaban or Phenprocoumon, it will be assessed whether patients received any of the relevant substances in the 90 days before the Index date.
 
For a list of medications with interaction potential see Table 12.

CHA ₂ DS ₂ -VASc Score	continuous	
The CHA₂DS₂-VASc score will be derived by assigning one point each for hypertension, diabetes mellitus, and heart failure, vascular disease (peripheral artery disease, myocardial infarction, aortic plaque), age 65-74 years, female sex and two points for age 75 years or older, previous stroke or transient ischemic attack (TIA), with a total possible score of nine [Trappe 2012].
 
Ambulatory verified as well as primary and secondary hospital discharge diagnoses within in the 12 months before the index date will be used to assess the CHA₂DS₂-VASc score.
 
For a complete list of all ICD-10 codes which will be used to form the CHA₂DS₂-VASc score please refer to Annex 2. Tables.

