- **Pharmaceutical Claims:** Contains drug dispensed by PZN (package level) – this is mapped to ATC codes and DDDs, day of prescription, day of dispensing, and costs of drugs dispensed from a statutory health insurance perspective without individual deductibles between single sickness funds and pharmaceutical companies. Furthermore, the type of doctor prescribing (e.g. cardiologist, general practitioner) is included.
- **Devices and Aids:** Contains type of device/aid (code and text) (e.g. massage, occupational therapy, walker, wheel chair), quantity prescribed, type of care provider, start and end date, and costs of device/aids.
- **Incapacity to Work and Sick Leave Payments:** This includes ICD-10-GM diagnoses that cause sick leave, duration of sick leave, and the corresponding start and end date of sick leave. In addition, the type of physician that filled-out the sick leave (e.g., cardiologist, general practitioner) and the cost of sick leave payments are incorporated.

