9.7.1.2 Primary and secondary objectives

The incidence rate and corresponding confidence intervals of the primary and secondary endpoints will be estimated as the number of events per 100 person years (% per year). Cox proportional hazard regression will be used to estimate unadjusted and adjusted hazard ratios (multivariate adjusted as well as 1:1 propensity matched). For all models, hazard ratios (HRs), 95% confidence intervals (CIs) and all other regression coefficients will be reported.

Kaplan-Meier curves will be generated to evaluate the time-to-first event associated with the initial treatment.

Rivaroxaban will be compared to Phenprocoumon. Hence, Phenprocoumon will be the reference category in the analysis. A subset of the variables depicted in Table 2 which were selected on an empirical basis, will be included as covariates in the Cox proportional hazards model.

Propensity Score Matching

In this study, we will additionally use propensity score matching. The propensity score will be calculated as the predicted probability of exposure (i.e. probably of receiving Rivaroxaban), given all that is known about a patient (i.e. patient characteristics and covariates).

The probability itself will be derived from a multivariate logistic regression using the parameters thought to act as confounding variables. The propensity score act as a “balancing score” in that all factors that contribute to the score are expected to be independent between treatment groups if the patient population is matched on propensity score and a stratified table of patient characteristics is examined. That is, after propensity score matching all other factors included in the score are expected to be balanced between the two treatment groups. This will minimize confounding by observed baseline covariates by removing any potential relationship between cofounders and exposure group.

In this study, we will estimate propensity scores from all measured factors noted above. These factors will be entered into a logistic regression model, with the factors as the independent variables (with no further variable selection) and the treatment as the dependent variable. From the resulting model, we will predict probability of treatment for each patient; this probability of treatment will be each patient’s estimated propensity score.

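### The closed covariate list uses nothing from the Devices and Aids file, so residual confounding by frailty or limited mobility is larger than it need be and is not acknowledged

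*Protocol*

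**What the plan says.** **Data held.** In the Protocol, section 9.4 (structure of the database), the Devices and Aids file is described thus: "Contains type of device/aid (code and text) (e.g. massage, occupational therapy, walker, wheel chair". It also carries quantity and start and end dates.

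**Propensity score.** Section 9.7.1.2 states: "In this study, we will estimate propensity scores from all measured factors noted above", entered "with the factors as the independent variables (with no further variable selection". The factors noted are those of section 9.3.1 and Table 2.

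**Adjusted Cox model.** The same section takes as covariates "A subset of the variables depicted in Table 2 which were selected on an empirical basis".

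**Existing correlates of frailty.** Section 9.3.1 and Table 2 include age and, as health care proxies, the number of unique medications and a count of hospital stays ("Total number of hospitalizations, independent of admission diagnosis, during the baseline period"). They also include two comorbidity indices, dementia, heart failure and renal stages. Table 8 gives hemiplegia a weight of 2 in both indices.

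**Limitations.** Section 9.9 concedes that patients cannot be characterised by clinical parameters. A separate bullet, on lifestyle variables, expects matching to balance "measured confounders (some of which will strongly correlate with unmeasured factors". Neither mentions frailty or mobility.

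**No later document.** Section 9.7 says there will be no separate SAP, and Annex 1 lists no stand-alone documents.

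**The concern.** Frailty or limited mobility may plausibly influence both the choice of anticoagulant and the risk of stroke or ICH. Section 7 names the monitoring burden of VKA as a limit on its use, which suggests one route by which mobility could affect the choice. That is inference; the protocol reports no channelling in either direction.

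No listed covariate measures physical function directly, yet the protocol describes a file that bears on it. Nothing else in the plan would reveal an imbalance. The diagnostics in section 9.7.1.2 (overlap plots, c-statistics, standardised differences) see only what was measured, and the sensitivity analyses concern dose and prior events. Matched cohorts could look balanced while differing in mobility, and both primary hazard ratios would carry the difference.

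**Working it through.** The plan gives no figure on this point to reproduce. The check has two parts.

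**1. Data inventory against covariate list**

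| Place in the Protocol | Content | Aid or device variable? |
|---|---|---|
| 9.4, structure of the database | Devices and Aids file, dated | Held |
| 9.2 | Inpatient, outpatient, prescriptions | No |
| 9.3.1 and Table 2 | Covariates | None |
| Tables 10 and 13 | Comorbidities, co-medications | None |
| Table 15 | Available variables of interest | None |
| 9.7.1.2, propensity score | Factors noted earlier, no further selection | None can enter |
| 9.7.1.2, Cox model | Subset of Table 2 | None can enter |
| 9.9 | Limitations | Frailty not named |

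**2. Scale, on assumed inputs**

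The protocol gives no prevalence of aid use, no association with outcome and no direction of channelling. All inputs in the next table are assumptions.

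For a binary factor with prevalence p1 in the rivaroxaban group, p0 in the phenprocoumon group and outcome rate ratio RR, the crude bias factor is

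B = [1 + p1(RR − 1)] / [1 + p0(RR − 1)]

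| p1 vs p0 | RR 1.5 | RR 2 | RR 3 |
|---|---|---|---|
| 8% vs 12% | 1.04/1.06 = 0.981 | 1.08/1.12 = 0.964 | 1.16/1.24 = 0.935 |
| 10% vs 15% | 1.05/1.075 = 0.977 | 1.10/1.15 = 0.957 | 1.20/1.30 = 0.923 |
| 10% vs 20% | 1.05/1.10 = 0.955 | 1.10/1.20 = 0.917 | 1.20/1.40 = 0.857 |

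Swapping the groups gives the reciprocals, from 1/0.981 = 1.019 to 1/0.857 = 1.167.

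For context, section 9.5 uses stroke hazard ratios of 0.94, 0.86 and 0.65. Dividing an observed value by B:

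- 0.94 corresponds to 0.94/0.981 = 0.958 up to 0.94/0.857 = 1.097. With channelling reversed, it corresponds to 0.94 × 0.981 = 0.922 down to 0.94 × 0.857 = 0.806.
- 0.86 corresponds to 0.86/0.981 = 0.877 up to 0.86/0.857 = 1.003. Reversed, it corresponds to 0.844 down to 0.737.
- The weakest ICH hazard ratio in section 9.5, 0.71, would reach at most 0.71/0.857 = 0.828.

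The E-value, 1/HR + √[(1/HR)(1/HR − 1)], is the strength of association that an unmeasured factor would need with both treatment and outcome to explain a hazard ratio fully:

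- Stroke: 1.32 for 0.94, 1.60 for 0.86 and 2.45 for 0.65.
- ICH: 2.17 for 0.71, 2.97 for 0.56 and 3.18 for 0.53.

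Modest residual confounding could therefore matter for the smaller stroke effects, and much less for the ICH effects.

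**The case against.** The strongest objection is that a claims study can almost always add another proxy, and nothing here is misstated. Several parts of it stand.

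- **Frailty is partly controlled.** A reader might infer that frailty is left uncontrolled. The covariates listed above, hemiplegia among them, do not support that; only a residual part is at issue.
- **The 9.9 sentence concerns lifestyle factors such as smoking.** Applying it to frailty is an inference of this review.
- **No promise is broken.** A reader might take "given all that is known about a patient (i.e. patient characteristics and covariates" as a commitment to use every file held. It is a general definition of a propensity score, qualified at once by its own parenthesis.
- **Walkers and wheelchairs are only examples in section 9.4.** The protocol gives no prevalence, completeness or validity for them, so they cannot be called the best frailty measure in the data.
- **The bias factors rest wholly on assumptions.** They are crude, before conditioning on other covariates. They are not upper bounds in general, since larger inputs give larger factors.

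Two replies remain. The list is closed and section 9.7 rules out a later SAP, so deferral is no answer. The protocol also already accepts the use of proxies, and one more from a file it describes is a specific and inexpensive step.

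**Conclusion.** The point holds as a cheap improvement, not as an error that invalidates the analysis. The propensity score and the Cox model use nothing from a dated, patient-level file that the protocol says exists. Residual confounding by frailty or limited mobility is therefore avoidably larger than it need be, and section 9.9 does not acknowledge it.

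The documents establish neither its size nor its direction. On the assumed inputs (8–10% against 12–20%, rate ratio 1.5 to 3), the crude factor is about 0.98 to 0.86, or about 1.02 to 1.17 if channelling is reversed, before the existing covariates absorb part of it. A reader might infer from the first range that the plan favours rivaroxaban. Nothing in the protocol supports that direction over the other.

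**What to change.** Add a row to Table 2: *Mobility aid (categorical): at least one walker or wheelchair claim whose start–end interval overlaps the 365 days before the index date.* Overlap is needed because requiring a start date inside the window would class a patient still using an aid issued earlier as a non-user.

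Enter the variable in the propensity score and in the pool of Cox covariates, and report its standardised difference before and after matching in Table 30. Name frailty as a limitation in section 9.9.

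The cost is one file to extract beyond the sectors named in section 9.2, and a one-time grouping of device codes and text. The variable will be imperfect: some aids may follow hip or knee replacement, which is excluded only for the 60 days before index. If it proves balanced, the sponsor has some evidence on physical function, which the plan does not otherwise measure directly. If not, matching and adjustment can reduce the imbalance.
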